#### D-3 Analysis Methods

The prior distributions discussed in Section D-2 will be combined with the observed data in the trial to obtain posterior distributions for the treatment and control groups. The probability of Treatment mean – Control mean < 0 given the observed data i.e.,  $P(\mu_T - \mu_C < 0|Data)$  will be calculated.

Let  $D = (x_1, \dots, x_n)$  be the data and  $x_i \sim N(\mu, \sigma^2)$ . Then  $\bar{x} \sim N(\mu, \frac{\sigma^2}{n})$ . If  $\sigma^2$  is a constant, we have the likelihood for the data

$$L(\mu|D) = p(D|\mu) \propto N(\bar{x}, \frac{\sigma^2}{n}).$$

The conjugate prior for  $\mu$  is supposed to be

$$p(\mu) \propto N(\mu_0, \sigma_0^2)$$

Then the posterior is given by

$$p(\mu|D) = L(\mu|D)p(\mu) \propto N(\mu_n, \sigma_n^2) \text{ where}$$
$$\mu_n = \frac{\sigma^2}{n\sigma_0^2 + \sigma^2} \mu_0 + \frac{n\sigma_0^2}{n\sigma_0^2 + \sigma^2} \bar{x} \text{ and}$$
$$\sigma_n^2 = \frac{1}{\frac{n}{\sigma^2} + \frac{1}{\sigma_0^2}} = \frac{\sigma^2 \sigma_0^2}{n\sigma_0^2 + \sigma^2}.$$

If  $P(\mu_T - \mu_C < 0|Data) > 0.95$ , the treatment group will be claimed as significantly better than the control group. This is equivalent to the hypothesis test of  $\mu_T - \mu_C = 0$  at one-sided  $\alpha = 0.05$  significant level.

Notice that  $(\mu_0, \sigma_0^2)$  are prior parameters determined from historical data borrowing and meta-analysis (see Section D-2).  $(\bar{x}, \frac{\sigma^2}{n})$  are LSMean and SE from MMRM based on data in the study. For treatment group, a "flat" non-informative prior probability distribution will be assumed, that is the posterior distribution is totally based on the observed data.

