7.3 Statistical Analyses for Efficacy

Primary Endpoint Analysis

The primary endpoint is change from baseline in DAS28-CRP at Week 12.

The first primary analysis is to test the superiority of ABBV-599 compared to placebo at Week 12.

The second primary analysis is to test a pre-specified set of dose-response models (detailed in the SAP) among ABBV-105 dose groups and the placebo group at Week 12 using the Multiple Comparison Procedure – Modeling (MCP-Mod) method.^{9,10}

Hypothesis testing in the primary analyses will be performed in a ranked fashion based on one-sided significance level of α = 0.05. The other analysis for the primary endpoint includes testing the superiority of ABBV-599 compared to each ABBV-105 dose group, as well as to upadacitinib. Additionally, each ABBV-105 group will be compared vs placebo group. All tests will be performed as

pairwise comparison at one-sided statistical significance level α = 0.05. The listing of these analyses is as follows:

- ABBV-599 vs placebo
- ABBV-105 dose response
- ABBV-599 vs each ABBV-105 dose
- Each ABBV-105 dose vs placebo
- ABBV-599 vs upadacitinib

In the analyses, the treatment mean will be estimated using least squares (LS) mean from Mixed-Effect Model Repeated Measurements (MMRM) method. One MMRM model including all treatment groups up to visit Week 12 data modeling will be used. Comparable historical placebo and upadacitinib data will be used to enhance the statistical power in relevant comparison analyses, which are detailed in the SAP.

Secondary Endpoints Analysis

Continuous efficacy variables will be analyzed using an MMRM method. It will be used for primary inference purpose. Categorical efficacy variables will be analyzed using the Cochran-Mantel-Haenszel (CMH) test controlling for stratification variables. Non-responder imputation (NRI) will be used for primary inference purpose and as observed (AO) analyses will be used for sensitivity analysis for selected endpoints.

Missing Data Imputation Definition

Non-Responder Imputation: An NRI approach will categorize any subject who has missing value for categorical variables at a specific visit as non-responder for that visit. In addition, subjects who prematurely discontinue from study drug will be considered as non-responders for all subsequent visits after discontinuation.

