## 8.3.3 Primary Efficacy Analyses

The first primary analysis is to test the superiority of ABBV-599 compared to placebo at Week 12 using MMRM (see Section 8.3.5.1). Two-sided 0.1 is to be used throughout in all efficacy analysis.

The second primary analysis is to test a pre-specified set of dose-response models among ABBV-105 dose groups and the placebo group at Week 12 using the Multiple Comparison Procedure – Modeling (MCP-Mod) method with borrowing historical placebo data (see Section 8.3.5.3).

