## 8.3.5 Details for Primary Efficacy Analysis

### 8.3.5.1 Mixed-Effect Model Repeated Measure (MMRM) for Pair-Wise Comparison

In the pair-wise comparison analyses without historical data borrowing, the treatment mean will be estimated from MMRM method. One MMRM model including all treatment groups up to visit Week 12 data will be used.

MMRM analysis will be conducted for primary endpoint. Data collected after a subject discontinues study drug will be considered as missing. The mixed model includes the categorical fixed effects of treatment, visit and treatment-by-visit interaction, prior bDMARD use, and baseline DAS28 (CRP) measurement. An unstructured variance covariance matrix will be used. The parameter estimation will be based on the assumption of data being missing at random and using the method of restricted maximum likelihood (REML).

Least-square mean (SE) and 90% confidence interval (CI) at Week 12 for each treatment group will be presented together with between treatment difference of least-square means (SE), 90% CI and p-value from t-test for the difference = 0.

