#### • ABBV-105 vs Placebo (Borrowing Placebo)

Historical data for placebo group consists of 349 subjects from three clinical trials with similar populations, similar inclusion and exclusion criteria; and they were conducted in a similar way as the current study. A meta-analysis shows that predicted mean (SD) and 95% confidence interval for mean are -0.80 (1.5) and [-1.06, -0.54].

In the ABBV-105 vs Placebo comparisons, 20 historical placebo subjects will be borrowed, which targets control of Bayesian type I error rate/False Positive Rate < 10%

and not exceeding study placebo sample size of 20. That is:  $n_h = 20$ ,  $\mu_h = -0.80$  and its

SE  $\sigma_h = 1.5/\sqrt{20} = 0.335$ . Therefore a conjugate prior distribution for placebo would be N (-0.80, 0.335). For ABBV-105, a "flat" non-informative prior probability distribution will be assumed, resulting in the posterior distribution totally based on the data. For supportive analysis, the dynamic borrowing based on observed bias may be performed as detailed in Appendix D.

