## 8.3.5.3 Dose-Response Modeling for ABBV-105

The dose-response relationship among ABBV-105 dose groups and the placebo group will be characterized for the primary endpoint using the Multiple Comparison Procedure - Modeling (MCP-Mod) method [Pinheiro 2006, Bretz 2005]. The response based on the primary analysis approach above will be used, and ADDPLAN DF software will be used to perform the MCP-Mod analyses. The posterior mean (SD) for placebo group (i.e., with

historical borrowing) will be used as primary analysis. The data directly from MMRM for placebo will also be analyzed as sensitivity analysis.

A set of 6 pre-specified standardized candidate dose-response models, as described in Table 1 will be utilized to examine the dose-response relationship. A statistically significant dose-response relationship will be declared if at least one model is identified by the MCP-Mod method to be statistically significant at  $\alpha = 0.1$  two-sided. The fitted dose-response curves will be presented graphically for all statistically significant models along with confidence bands. The minimum effective dose (MED) will be identified for each statistically significant model based on the pre-specified clinical meaningful target of -0.88. The weighted MED across all significant models will be calculated, with weight being inverse of model AIC.

Model	$f(d, \theta)$ d = dose, $\theta$ = Model Parameters	f  (d, θ) Standardized Model	Initial Value(s) for Parameter(s)
Linear	$E_0 + \delta d$	d	NA
Exponential	$E_0 + E_1\left[exp\left(\frac{d}{\delta}\right) - 1\right]$	$exp\left(rac{d}{\delta} ight)-1$	$\delta = 20$
Logistic	$E_0 + \frac{E_{max}}{1 + exp\left(\frac{ED_{50} - d}{\delta}\right)}$	$\frac{1}{1 + exp\left(\frac{ED_{50} - d}{\delta}\right)}$	$ED_{50}=5,\delta=10$
EMax	$E_0 + \frac{E_{max}d}{ED_{50} + d}$	$\frac{d}{ED_{50}+d}$	$ED_{50} = 5$
sigEMax	$E_0 + \frac{E_{max}d^h}{ED_{50}^h + d^h}$	$\frac{d^h}{ED_{50}{}^h + d^h}$	$ED_{50} = 5, h = 2$
Quadratic	$E_0 + \beta_1 d + \beta_2 d^2$	$d + \frac{\beta_2}{ \beta_1 } d^2$	$\delta = -0.01$

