## 12.0 Overall Type-I Error Control

Hypothesis testing in the primary analyses (see Section 8.3.3) will be performed in a ranked fashion as follows based on two-sided significance level of  $\alpha = 0.1$ .

- 1) The superiority of ABBV-599 compared to placebo at Week 12 using MMRM.
- The dose-response among ABBV-105 dose groups and the placebo group at Week 12 using MCP-Mod method.

All other tests will be performed at two-sided statistical significance level of  $\alpha = 0.1$  without multiple testing  $\alpha$  adjustment.

Since there are no efficacy analyses for early stopping planned for the DMC review, no alpha spending is needed due to the DMC review.

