#### Figure D-2. Meta-Analysis for Historical Upadacitinib Data

In addition, upadacitinib-Phase III study data becomes available after this study design. A sensitivity analysis will be performed to include placebo data from upadacitinib-Phase III study in the meta-analysis (n = 144, mean (SD) = -1.01 (1.3)).

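### SAP D-3 and Section 12 state a one-sided 0.05 level for tests that borrow historical controls, but at a given true bias that level does not hold, and no false positive rate is given for the borrowed MCP-Mod test

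*SAP*

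**What the plan says.** Four parts of the plan bear on the level.

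- **Decision rule (SAP Appendix D-3).** If the posterior probability that the treatment mean is below the control mean exceeds 0.95, "the treatment group will be claimed as significantly better than the control group. This is equivalent to the hypothesis test of" no difference at one-sided 0.05.
- **Error control (SAP Section 12).** "Hypothesis testing in the primary analyses (see Section 8.3.3) will be performed in a ranked fashion as follows based on two-sided significance level of" 0.1. ABBV-599 vs placebo by MMRM comes first and the ABBV-105 dose-response by MCP-Mod second. Protocol 7.3 gives the same level in one-sided form: testing "will be performed in a ranked fashion based on one-sided significance level of" 0.05.
- **Which version is primary.** SAP 8.3.3 defines the second primary analysis as the MCP-Mod "method with borrowing historical placebo data". SAP 8.3.5.3 confirms that the placebo posterior (with "historical borrowing) will be used as primary analysis. The data directly from MMRM for placebo will also be analyzed as sensitivity analysis"). Step 3 of the MCP-Mod procedure says the familywise error rate is preserved and does not mention borrowing.
- **What is disclosed about borrowing.** SAP 8.3.5.2 borrows 20 placebo subjects, "which targets control of Bayesian type I error rate/False Positive Rate < 10"%. Table D-2 lists pairwise false positive rates by relative bias r, and Appendix D-2 takes 0.26 DAS28 points (r of 0.31) as a reasonable limit for the bias.

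**The concern.** The same rule is called equivalent to a 5% test in D-3 and shown to have a 7.1% false positive rate in Table D-2, at a bias inside the SAP's own limit. Both cannot be true of the rate at a given true placebo mean.

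The problem reaches a ranked primary test. MCP-Mod has its own significance rule, but it takes the same borrowed placebo mean and SD, and Section 12 states its level without qualification and without reference to Appendix D. Tables D-2 and D-3 are pairwise only, so a reader cannot find the error rate behind a claim of significant dose-response. That claim matters because the study is meant to define doses for further development.

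The inflating direction is historical placebo improving less than concurrent placebo. The SAP names data on that side of the prior mean: the later Phase III upadacitinib study had a placebo change of -1.01 (n = 144, SD 1.3), against a prior mean of -0.80.

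**Working it through.** Bias below means historical minus concurrent placebo mean. A positive bias favours ABBV-105.

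**Inputs.** 40 subjects per ABBV-105 arm, 20 concurrent and 20 borrowed placebo, SD 1.5 (SAP 2.4, 8.3.5.2). Borrowed share a0 = 20/(20+20) = 0.5. For Table D-2: k = 2, alpha = 0.05, 1-beta = 80%, delta = 0.85. Bias limit 0.26 (D-2).

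**Reproducing Table D-2 with SAP formula (1).** The normal quantiles are 1.645 and 0.842, sum 2.486.

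- Bias term at r = 0.3: √2 × 0.3 × 0.5 × 2.486 = 0.527
- Threshold term: 1.645 × √(1 + 2 × 0.5) = 2.326
- Denominator: √(1 + 2 × 0.25) = 1.225
- Plus direction: Φ[(0.527 − 2.326)/1.225] = 7.1%
- Minus direction: Φ[(−0.527 − 2.326)/1.225] = 1.0%

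Both match the table. The same formula gives 2.9% at r = 0 and 7.3% at r = +0.31.

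**Direct calculation on the bias scale, pairwise.** The rate is Φ[(a0 × bias − 1.645 × SE_post)/SE_true], with

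- SE_post = 1.5 × √(1/40 + 1/40) = 0.335, the standard error the rule uses
- SE_true = 1.5 × √(1/40 + 0.5²/20) = 0.290, the sampling standard error when the historical mean is fixed

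Setting the rate to 5% gives bias = (1.645/0.5) × (0.335 − 0.290) = about +0.15.

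**Why 5% holds on average.** If the bias is drawn from the analysis prior, N(0, 0.335²), the numerator gains variance 0.25 × 0.335² = 0.028. Then SE_true² + 0.028 = 0.084 + 0.028 = 0.1125 = SE_post², and the average rate is Φ(−1.645) = 5.0%.

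**Borrowed MCP-Mod.** Simulated with 2,000,000 draws: doses 0/5/20/60, the six Table 1 models, optimal contrasts, normal approximation, SD 1.5, placebo posterior treated as n = 40, critical value 1.95.

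| Bias | Pairwise ABBV-105 vs placebo | Borrowed MCP-Mod |
|---|---|---|
| −0.26 | 0.9% | 1.8% |
| 0 | 2.9% | 3.4% |
| +0.21 | 6.2% | 5.9% |
| +0.26 | 7.3% | 6.8% |
| averaged over analysis prior | 5.0% | 5.0% |

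MCP-Mod also crosses 5% at about +0.15. Unborrowed MCP-Mod gives 5.0% whatever the bias. At +0.26 the borrowed rate stays at 6.7% to 6.8% with 15% missing data or an in-trial SD of 1.3 or 1.7.

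**The +0.21 row.** −0.80 − (−1.01) = +0.21, or r = 0.21/0.85 = 0.25. The 95% interval of that Phase III mean is −1.01 ± 1.96 × 1.3/√144, about −1.22 to −0.80, so this illustrates the direction and does not prove bias.

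**ABBV-599 vs upadacitinib (additional analysis, 60 vs 40 + 40, SD 1.5).** The same calculation gives 1.0% / 3.2% / 8.3% at bias −0.215 / 0 / +0.215, and 5.0% averaged over its prior. Table D-3 prints 9.3% at r = 0.65. Its 39% power input implies 2 × (1.645 − 0.279)² × 1.5²/0.33² = 77 per arm, while 60 per arm gives 33%.

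**The case against.** **Disclosure.** The inflation was the criterion for choosing how many subjects to borrow: the < 10% target is in the main SAP text, Table D-2 prints the rates, and D-3 follows directly on them. This stands for the pairwise comparisons. It does not cover MCP-Mod, and it leaves the 0.05 statements in D-3 and Section 12 uncorrected.

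**The 0.95 rule is not the ranked test's rule.** It governs pairwise comparisons that SAP 8.3.4 lists as additional and Section 12 leaves unadjusted. This is correct. There are two linked defects: the D-3 sentence for the pairwise tests, and the unqualified Section 12 level for MCP-Mod.

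**The expected error is below nominal on the sponsor's evidence.** The prior is deliberately discounted, with 20 borrowed against an effective sample size of 49. Averaging over the SAP's predictive distribution instead (SD = √(0.0297 + (0.26/1.96)²), about 0.217) gives 3.8% pairwise and 4.1% for MCP-Mod. This is useful context, but it is still an average and does not make 0.05 the rate at a given bias.

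**The −1.01 figure is selective.** Pooling it with the three earlier studies moves the mean only to −0.86. A bias of +0.06 gives 3.6% pairwise and 4.0% for MCP-Mod. This stands as a caution against reading the +0.21 row as a forecast. The SAP already plans that meta-analysis: "A sensitivity analysis will be performed to include placebo data from upadacitinib-Phase III study in the meta-analysis".

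**The effect is small, in an exploratory Phase 2 study.** This stands, and it limits the weight of the point.

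**Conclusion.** The concern holds. The plan states a one-sided 0.05 level that its borrowed tests do not have at a given true difference between historical and concurrent control, and Appendix D contradicts the statement. Over the SAP's own bias range of ±0.26, the pairwise ABBV-105 test runs from 0.9% to 7.3% and borrowed MCP-Mod from 1.8% to 6.8%. Both are conservative at zero or negative bias and exceed 5% only above about +0.15. For the ranked test the excess is at most about 1.8 points.

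The first ranked test is unaffected, because it uses the MMRM without borrowing ("In the pair-wise comparison analyses without historical data borrowing, the treatment mean will be estimated from MMRM method").

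The MCP-Mod figures rest on a normal approximation, SD 1.5 and our implementation of the contrasts, so the sponsor's software may differ slightly. The pairwise figures follow from the SAP's own formula. The point should be fixed before unblinding, but it does not threaten the design.

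**What to change.** 1. **D-3.** Replace the equivalence sentence with text such as: *Conditional on a given difference between historical and concurrent control, this rule does not have a one-sided 0.05 false positive rate; see Tables D-2 and D-3. The 0.05 level holds on average over the assumed prior.*
2. **Section 12.** State that the nominal level applies to tests without borrowing and that borrowed tests have bias-dependent rates (target < 10%), with a cross-reference to Appendix D. Qualify the familywise error statement in the MCP-Mod steps in the same way.
3. **Appendix D.** Add a sponsor simulation of the false positive rate and power of borrowed MCP-Mod for bias between −0.26 and +0.26, as implemented in the planned software, and quote the range in Section 12. At the same time, check Table D-3's 39% power input against 60 per arm. That is a side item and does not affect the conclusion.
4. **Reporting.** Show the planned unborrowed MCP-Mod result beside the borrowed one, identified as the analysis at the nominal level.

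The cost is SAP wording and one simulation before unblinding. Patients, thresholds, decision rules and power are unchanged. The downside is that the stated error rate becomes slightly less favourable.
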